7.3.7.3 Special Reporting of Liver Events

A liver dysfunction details eCRF will be utilized during the study. The type of information needed to complete it is provided in Appendix 4 ([Section 13.4](#)). The purpose of the liver dysfunction details eCRF and additional testing is to facilitate review of each subject who develops liver chemistry test abnormalities and/or signs or symptoms of liver dysfunction during the study to determine the probable cause(s) of these abnormalities. The review will be performed by an independent HERC using DILIN probability criteria, modified (0 to 5% = unrelated; 6 to 25% = unlikely, 25% to 50% = possibly, 51% to 75% = probably, 76% to 95% = very likely, >95% = definite) (Fontana RJ 2009).¹⁸ The HERC will independently decide attribution and will communicate in writing with the sponsor. The results of the HERC review will be used in assessing the primary and secondary endpoints. The result of these analyses may be presented separately from the final clinical study report (CSR).

The Investigator must complete the liver dysfunction details eCRF and submit it within 24 hours of awareness through the SAE reporting pathway (described in [Section 7.3.8.3](#)) for any subject who develops an Adverse Event of Special Interest (AESI) related to abnormal liver chemistry test results or clinical signs or symptoms. Specifically, any subject who

- develops any signs or symptoms of hepatic dysfunction (see Appendix 4 [[Section 13.4](#)])
- discontinues treatment due to a liver-related AE,
- reports a serious liver-related AE,
- develops ALT or AST levels $>3 \times$ ULN,
- develops total bilirubin levels $>2 \times$ ULN.

The AESI report form should be updated as new information becomes available.

7.3.8 Adverse Events

7.3.8.1 Definitions of Adverse Events

The Investigator is responsible for reporting all AEs that are observed or reported during the study, regardless of their relationship to study drug or their clinical significance, as outlined in [Section 7.3.8.2](#) below.

An AE is defined as any untoward medical occurrence in a subject enrolled into this study regardless of its causal relationship to study drug.

A treatment-emergent AE (TEAE) is defined as any event not present before exposure to study drug or any event already present that worsens in either intensity or frequency after exposure to study drug.

An SAE is defined as any event that results in death, is immediately life threatening, requires in-subject hospitalization or prolongation of existing hospitalization, results in persistent or significant disability/incapacity, or is a congenital anomaly/birth defect. Important medical events that may not result in death, be life threatening, or require hospitalization may be considered SAEs when, based upon appropriate medical judgment, they may jeopardize the subject or may require medical or surgical intervention to prevent one of the outcomes listed in this definition.

Hospitalization does not include admissions for treatment of a pre-existing condition, including surgery, not associated with a new AE; respite care; social reasons; administrative reasons; skilled nursing care; rehabilitation; hospice; or same-day surgery.

7.3.8.2 Eliciting and Documenting Adverse Events and Serious Adverse Events

All SAEs will be recorded from the time the ICF is signed until study completion. Non-serious AEs will be recorded from the start of study treatment until study completion. Other changes in health or new symptoms occurring during the Screening or Baseline Periods will be recorded as medical history.

At every study visit, subjects will be asked a standard non-leading question to elicit any medically related changes in their well-being. They will also be asked if they have been hospitalized, had any accidents, used any new medications, or changed concomitant medication regimens (both prescription and over-the-counter medications).

In addition to subject observations, any abnormal laboratory test results (hematology, clinical chemistry, or urinalysis) or other safety assessments (e.g., ECGs, radiological scans, vital sign measurements, physical examination findings), including those that worsen from baseline, deemed to be CS in the medical and scientific judgment of the Investigator are to be recorded as AEs or SAEs.

7.3.8.3 Reporting Adverse Events, Serious Adverse Events, and Adverse Events of Special Interest

All AEs reported or observed during the study will be recorded on the AE page of the eCRF. Information to be collected includes drug treatment, dose, event term, date of onset, Investigator-specified assessment of severity and relationship to study drug, date of resolution of the event, seriousness, any required treatment or evaluations, and outcome. AEs resulting from concurrent illnesses, reactions to concurrent illnesses, reactions to concurrent medications, or progression of disease states must also be reported. All AEs will be followed to adequate resolution.

Any medical condition that is present at the time the subject is screened or during baseline, i.e., medical history, but does not deteriorate should not be reported as an AE. However, if it deteriorates at any time during the study, it should be recorded as an AE.

However, any safety assessments that are associated with the underlying disease, unless judged by the Investigator to be more severe than expected for the subject's condition, are not to be reported as AEs or SAEs.

For the purpose of this study, liver events are considered to be AESIs. Liver events will be reported directly from the electronic data capture [EDC] system.

Pregnancy events will need to be reported on special pregnancy forms to ICON PVSS.

Any AE that meets SAE or AESI criteria will be reported to ICON Pharmacovigilance & Safety Services (PVSS) immediately (i.e., within 24 hours) after site personnel first learn about the event. Investigators should record all SAE/AESI details available, including Investigator causality assessment, on an Adverse Event eCRF or appropriate AESI forms and submit the report via the electronic data capture (EDC) system within 24 hours of becoming aware of the event. Notification of SAE/AESI entry will be generated and sent to ICON PVSS via the EDC system. Pregnancy events will also be reported to ICON PVSS within 24 hours of recognition of the event, but on the special forms provided.

In the event the EDC system is unavailable, a completed SAE Report Form should be submitted to ICON PVSS as an email attachment or by fax to the email address / fax number below. The EDC system must be updated with the information on the paper report as soon as the EDC is available. The preferred method of reporting on paper is via email:

ICON PVSS Email Address: [contact]

or via fax to:

7.3.8.5 Assessment of Causality

The Investigator’s assessment of causality must be provided for all AEs. The causality is the determination of whether there exists a reasonable possibility that the study drug itself caused or contributed to an AE.

If the final determination of causality is unknown and the Investigator does not know whether the study drug caused the event, then the event will be handled as “possibly related to study drug” for reporting purposes. If the Investigator’s causality is “unknown, but not related to study drug”, this should be clearly documented on study records.

The relationship of an AE to the administration of the study drug will be assessed and recorded on the eCRF. Terms used to describe the degree of causality between a study drug/investigational product and an AE are: definitely, probably, possibly, unlikely, or not related. The best estimate at the time of reporting of the causal relationship between the experimental intervention and an AE and the degree of certainty about causality will be graded using the criteria specified in [Table 8](#).

Table 8 Guideline for Assessment of Adverse Event Causality

Relationship to Study Drug	Description
Not Related	The AE is clearly due to extraneous causes (e.g., underlying disease, environment) or exposure to the investigational product has not occurred. Such events MUST have an alternative, definitive etiology documented in the subject's medical record.
Unlikely Related	A potential relationship between study drug and the AE could exist (i.e., the possibility cannot be excluded), but the AE is most likely explained by causes other than the study drug (e.g., could readily have been produced by the subject's clinical state or could have been due to environmental or other interventions).
Possibly Related	The AE and administration of study drug are reasonably related in time and/or follow a known pattern of response, and the AE can be explained equally well by causes other than study drug (e.g., could readily have been produced by the subject's clinical state or could have been due to environmental or other interventions).
Probably Related	The AE and administration of study drug are reasonably related in time and/or follow a known pattern of response, and the AE is more likely explained by study drug than other causes.
Definitely Related	The AE and administration of study drug are related in time, and a direct association can be demonstrated (e.g., disappears or decreases with reduction in dose or cessation of drug/investigational product and recurs with re-exposure).

7.3.8.6 Follow-Up of Subjects Reporting Adverse Events

All AEs must be reported in detail on the appropriate page of the eCRF and followed to satisfactory resolution, until the Investigator deems the event to be chronic or not CS, or until the subject is considered to be stable.

7.3.8.7 Overdose Management

An overdose is any dose of study drug given to a subject or taken by a subject that exceeds the dose described in the protocol. Any overdose, with or without associated AEs, must be promptly reported to the Investigator and also reported to the Sponsor. Overdoses without signs or symptoms do not need to be recorded as AEs; in case of any AEs associated with the overdose, these should be reported on relevant AE/SAE sections in the eCRF. In the event of suspected overdose, the appropriate supportive clinical care including fluid replacement should be instituted at the discretion of the Investigator or as dictated by the subject's clinical status.

7.3.8.8 Pregnancy

Pregnancy is not regarded as an AE unless there is a medical/surgical complication. Any pregnancy of a subject or the partner of a subject that occurs during study participation must be reported using a clinical study pregnancy reporting form. To ensure subject safety, each pregnancy must be reported through this mechanism to ICON PVSS within 24 hours of learning of its occurrence.

The pregnancy must be followed-up to determine outcome (including spontaneous miscarriage, elective termination, normal birth, or congenital abnormality) and status of mother and child, even if the subject was discontinued from the study. Pregnancy

complications and terminations of pregnancy will be reported as an SAE if SAE criteria are fulfilled. Spontaneous miscarriages must be reported as an SAE.

Any SAE occurring in association with a pregnancy, brought to the Investigator's attention after the subject has completed the study, and considered by the Investigator as possibly related to the study treatment, must be promptly reported to ICON PVSS.

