4.1.1 Inclusion Criteria

In order to qualify for enrollment in this study, each subject must meet the following inclusion criteria:

1. Male or female, between 18 and 65 years of age (inclusive) at the time of Screening.
2. Female subjects must:
 - a. not be pregnant, lactating, or breastfeeding.
 - b. be either postmenopausal (defined as amenorrhea for ≥ 12 months), surgically sterile (defined as having undergone hysterectomy and/or bilateral oophorectomy), or if of child-bearing potential (WOCBP) must agree to practice appropriate methods of birth control or remain abstinent (only if this is the usual and preferred lifestyle of the participant) during the study and for 30 days after the last dose of study drug. Acceptable forms of contraception include any of the following:
 - hormonal contraceptives (i.e., oral, intravaginal, transdermal, injectable, implantable)
 - double barrier methods of non-hormonal contraception are permitted in this study.
 - male or female condom with spermicide (cream, spray, gel, suppository, contraceptive sponge, or polymer film)
 - diaphragm, cervical cap, or contraceptive sponge with spermicide (with or without a condom)
 - intrauterine device (IUD), including progestin-containing intrauterine devices
 - intrauterine hormone-releasing system (IUS)
 - male sexual partner who has been vasectomized for at least 3 months prior to Screening and who has obtained a follow-up negative sperm

count

- bilateral tubal ligation
 - Essure[®] procedure (tubal occlusion).
3. Male subjects and their female partners of childbearing potential must also use the contraceptive methods listed above or remain abstinent (only if this is the usual and preferred lifestyle of the participant) during the study and for 30 days after the last dose of study drug.
 4. Diagnosis of ADPKD confirmed by previous treatment with tolvaptan specifically for that indication and supported by evidence from any imaging modality or genetic analysis.
 5. Screening eGFR ≥ 20 ml/min/1.73m².
 6. Body mass index (BMI) between 18 and 35 kg/m² (inclusive) at the time of Screening.
 7. Documented history of:

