4.2.4 Reasons for Withdrawal

Reasons for withdrawal (subjects who refuse to return for any remaining study visits) or discontinuation (subjects who prematurely stop the treatment) at any time during the study may include, but are not limited, to the following:

1. No longer meet the protocol inclusion or exclusion criteria, e.g., require a prohibited concomitant medication.
2. Noncompliance with the protocol.
3. Lack of efficacy.
4. A serious or intolerable AE that, in the Investigator's opinion, requires withdrawal from the study, including but not limited to laboratory safety assessments that reveal clinically significant (CS) hematological or biochemical changes from the baseline values, other than changes that are expected for vasopressin antagonists, and symptoms of an intercurrent illness that justifies withdrawal. If the AE is related to abnormal liver chemistry test results, see [Section 7.3.7](#) for additional follow-up requirements. Mild elevations in serum creatinine or serum sodium are known pharmacodynamic effects of vasopressin antagonists like lixivaptan and are transient and reversible. Therefore, subjects should not be withdrawn from study participation solely due to mildly elevated serum creatinine or serum sodium. Cases where eGFR has declined by 25% or more from baseline should be discussed with the medical monitor and sponsor.
5. Death
6. Lost to follow-up.
7. Other (e.g., pregnancy, study burden, development of contraindication to use of study drug).
8. Withdrawal of consent (partial or complete).
9. Investigator's or Sponsor's decision to discontinue the subject's participation in the study.
10. Sponsor termination of the study.

Upon occurrence of an SAE or intolerable AE, the Investigator will confer with the medical monitor and Sponsor. If a subject is discontinued from study drug because of an AE, the

event will be followed until it is resolved or stable or up to 28 days as determined by the Investigator. Any subject may withdraw his or her consent at any time. Subjects' safety will be closely monitored throughout the study, and the study will be conducted following Good Clinical Practices (GCP). The entire study may be stopped at any time at the discretion of the Sponsor.

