6.5.3 Visit 27 (End of Study Visit)

Visit 27 is the last visit in this study and will occur 28±3 days after the last dose of study drug (Visit 24). The visit will be conducted in the clinic. The following procedures will be performed at Visit 27:

- Check vital signs (sitting blood pressure and heart rate)
- Perform a brief physical exam
- Perform a 12-lead ECG
- Check AEs and SAEs
- Collect and review concomitant medication information
- Process an aliquot of first morning, fasting urine for specific gravity
- Send the remaining first morning, fasting urine for U_{osm} determination
- Collect urine for urinalysis
- Collect urine sample for a urine pregnancy test in WOCBP
- Collect a blood sample for the following laboratory testing:
 - Complete chemistry panel
 - Liver chemistry panel
 - Hematology
- Contact the IRT to complete subject's participation in PA-ADPKD-303

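### Pregnancy reporting is limited to study participation, which can end before the protocol's own 30-day post-dose contraception window closes

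*Protocol*

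**What the plan says.** **Contraception.** Protocol Section 4.1.1, inclusion criterion 2, requires women of childbearing potential to use contraception or remain abstinent "during the study and for 30 days after the last dose of study drug". Criterion 3 applies the same period to men: "Male subjects and their female partners of childbearing potential must also use the contraceptive methods listed above". The synopsis agrees.

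**Reporting.** Section 7.3.8.8: "Any pregnancy of a subject or the partner of a subject that occurs during study participation must be reported". The report is due within 24 hours of the site learning of the pregnancy, and the pregnancy is then followed to outcome even if the subject has been discontinued. No post-dose interval is given. After a subject has completed the study, the section keeps one duty: to report a serious adverse event associated with a pregnancy that the investigator considers possibly related.

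**End of participation.** Section 6.5.3 places Visit 27, the last visit, at day 28 ± 3 after the last dose. Its final instruction to the site is "Contact the IRT to complete subject's participation in PA-ADPKD-303".

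**Early leavers.** Section 4.2.3 treats a subject who stops study drug as a study withdrawal unless followed for safety. Such subjects are encouraged, but not obliged, to attend the Early Termination visit and Visits 25 to 27. Section 4.2.4 describes withdrawal as refusal of all remaining visits.

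**The concern.** The contraception rule treats the 30 days after the last dose as a time when pregnancy should be avoided, both in female subjects and in partners of male subjects. The reporting rule is tied to a different endpoint, the end of participation, which can come first. A pregnancy that starts between the two dates is one the protocol asks subjects to prevent but does not ask sites to report.

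What is lost is outcome information on a pregnancy in the protocol's own precaution period. Scheduled testing does not close the gap: the last pregnancy test is at Visit 27, and partners are not tested, so a partner pregnancy is known only if the subject tells the site. The procedures listed for Visit 24/Early Termination and Visit 27 contain no instruction to do so.

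**Working it through.** **Inputs**

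- Contraception window: to day 30 after the last dose (Section 4.1.1).
- Visit 27: day 28 ± 3 after the last dose (Section 6.5.3).
- Visit 25: no earlier than day 8, +3 (Section 6.5.1; Table 1, footnote b).
- Visit 26: 7 to 14 days, ± 3, after Visit 25 (Section 6.5.2).
- Assumptions: the last dose coincides with Visit 24, as Table 1 and Section 6.5.3 imply. Participation ends at Visit 27 for completers and at last contact for subjects who decline further visits. The protocol does not define the term.

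**End of participation for completers.** 28 − 3 = day 25 to 28 + 3 = day 31.

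**Uncovered days** = max(0, 30 − d), where d is the day participation ends.

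| Participation ends at | d | Uncovered days |
|---|---|---|
| Visit 27, earliest | 25 | 30 − 25 = 5 |
| Visit 27, nominal | 28 | 30 − 28 = 2 |
| Visit 27, day 30 or 31 | 30, 31 | 0 |
| Visit 26, latest (11 + 14 + 3) | 28 | 30 − 28 = 2 |
| Visit 26, earliest (8 + 7 − 3) | 12 | 30 − 12 = 18 |
| Visit 25, latest (8 + 3) | 11 | 30 − 11 = 19 |
| Visit 25, earliest | 8 | 30 − 8 = 22 |
| Last dose, no later contact | 0 | 30 − 0 = 30 |

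**Does other text close the gap?**

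- The post-completion clause in Section 7.3.8.8 covers serious adverse events judged possibly related, so an uncomplicated pregnancy falls outside it. It also speaks of a subject who has completed the study, which Section 4.2.1 defines as through Visit 27. Read literally, it does not reach withdrawers.
- The outcome follow-up that survives discontinuation concerns a pregnancy that was already reportable. It does not widen which pregnancies qualify.
- Section 7.3.8.3 asks for pregnancy events to be reported within 24 hours of recognition and names no participation limit. However, that section opens with events reported or observed during the study, and it does not clearly override the specific limit in Section 7.3.8.8.

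**The case against.** The strongest opposing case is that the residual is narrow and mostly protected.

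- At the scheduled day 28 a completer has 2 uncovered days, and 5 only at the edge of the visit window. This stands.
- Early leavers are encouraged to complete about four weeks of follow-up (Section 4.2.3), and investigators must try to follow anyone who withdraws (Section 4.2.5). Thirty days is therefore the extreme, not the default. This also stands, but encouragement is not a requirement, and follow-up that does take place still ends at Visit 27.
- Congenital anomalies are serious by definition (Section 7.3.8.1), miscarriages must be reported as serious (Section 7.3.8.8), and an event of unknown causality is handled as possibly related (Section 7.3.8.5). Many consequential outcomes would therefore be captured after completion. What remains is mainly the uncomplicated pregnancy, together with subjects who withdrew rather than completed.
- For a subject who cannot be reached, no reporting rule yields information. True, but the rule decides what a site must do when it does find out.

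Three stronger readings are tempting, and the documents do not support them. A reader might infer that these pregnancies go unreported; the text only fails to require a report, and a site may still make one. A reader might infer that any pregnancy discovered after exit is lost; one that began during participation is still covered, because the 24-hour clock starts when the site learns of it. And a reader might take the 30 days as a stated period of fetal exposure; the protocol gives it only as a contraception requirement.

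**Conclusion.** The two windows do not match, and the passages should be reconciled. For completers the shortfall is 0 to 5 days. For early leavers it depends on last contact: 2 to 18 days if last seen at Visit 26, 19 to 22 days if last seen at Visit 25, and up to 30 days with no contact after the last dose. The early leavers are the substantive part.

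This rests on reading the Visit 27 system entry as the end of participation, which is the natural reading but not a formal definition. The expected number of pregnancies is not given and must be small with at most 50 subjects. SAP Section 9 records that the study was terminated early, that only 6 participants entered maintenance, and that most of those ended prematurely. Early exit was therefore real, though the SAP does not say whether follow-up was completed.

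No endpoint, analysis population or error rate depends on this. It is a minor but inexpensive safety-reporting improvement. No view is taken on whether 30 days is the right length; the point is only that the protocol's two rules should agree.

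**What to change.** In Section 7.3.8.8, extend the time limit to read: *that occurs during study participation or within 30 days after the last dose, whichever ends later, whether or not the subject is still in the study and whenever it becomes known*. Keep the 24-hour reporting and the follow-up to outcome.

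Do not replace the limit with a window running only from first dose to day 30. That would drop three groups the present wording covers:

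- pregnancies before the first dose, over up to 8 + 3 = 11 weeks of Screening and Baseline;
- pregnancies in subjects who stop drug but stay on the visit schedule beyond 30 days;
- day 31 for a completer with a late Visit 27.

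Add an instruction to notify the site of a pregnancy in the subject or a partner, given when drug is first dispensed (Visit 5) and repeated at Visit 24/Early Termination and Visit 27. Giving it at Visit 5 matters because a subject who leaves abruptly may never attend the later visits.

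The uncovered interval under the rule becomes 0 days for every treated subject. The cost is one sentence and a line of subject instructions, with no added visit or test.
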